#### *Nursing Guidelines*

Anti PD-L1 side effects vary greatly from those of traditional chemotherapy and can vary in severity from mild to life threatening. Instruct patients to report any side effects to the study team immediately. Side effects may be immediate or delayed up to months after discontinuation of therapy. Most side effects are reversible with prompt intervention of corticosteroids

Diarrhea can be common and can be very severe, leading to colonic perforation. Instruct patients to report ANY increase in the number of stools and/or change in baseline, blood in the stool, abdominal pain to the study team immediately.

Rash/pruritus/dermatitis is seen. Patients should report any rash to the study team. Treat per [Section 8.0](#) and monitor for effectiveness.

Monitor LFT's closely as elevations in these levels could indicate early onset autoimmune hepatitis. Patients should also be instructed to report any jaundice, or right upper quadrant pain to the study team immediately.

Pneumonitis can be seen and may be mild (only seen on imaging) to severe. Patients should be instructed to report any SOB, dyspnea, cough, chest pain, etc. to the study team immediately. Patients reporting these symptoms should have a pulse ox checked and consider immediate imaging per the treating MD.

Endocrinopathies (including hypopituitarism, hypothyroidism, hypophysitis, and adrenal insufficiency) are a concern given the mechanism of action of this agent. Patients may present only with the vague sense of fatigue and "not feeling well." Additional symptoms may be that of nausea, sweating and decreased activity tolerance. Instruct patients to report these signs or symptoms immediately and obtain appropriate labs as ordered by MD.

Pancreatitis is possible with anti PD-L1 therapy based on mechanism of action. Instruct patients to report abdominal pain, nausea and vomiting to the study team.

Patients who are started on steroid therapy for any side effects of anti PD-L1 toxicity should be instructed to take the steroids as ordered, and not to discontinue abruptly as symptoms may return and be severe. Patients may be on steroid therapy for weeks. Instruct patients to report any increase or change in side effects with any dosage decrease as patients may need a slower taper.

Female patients of childbearing potential should utilize contraception and take active measures to avoid pregnancy while undergoing atezolizumab treatment and for at least 150 days after the last dose of atezolizumab.

#### *Agent Inventory Records*

The investigator, or a responsible party designated by the investigator, must maintain a careful record of the receipt, dispensing, and final disposition of all agents received from the PMB using the appropriate NCI Investigational Agent (Drug) Accountability Record (DARF) available on the CTEP forms page. Store and maintain separate NCI Investigational Agent Accountability Records for each agent, strength, formulation and ordering investigator on this protocol.

*Investigator Brochure Availability*

The current versions of the IBs for the agents will be accessible to site investigators and research staff through the PMB OAOP application. Access to OAOP requires the establishment of a CTEP IAM account and the maintenance of an “active” account status, and a “current” password and active person registration status. Questions about IB access may be directed to the PMB IB Coordinator via email.

*Useful Links and Contacts*

- CTEP Forms, Templates, Documents: <http://ctep.cancer.gov/forms/>
- NCI CTEP Investigator Registration: [[contact]](mailto:[contact])
- PMB Online Agent Order Processing (OAOP) application: <https://eapps-ctep.nci.nih.gov/OAOP/pages/login.jsp>
- CTEP Identity and Access Management (IAM) account: <https://ctepcore.nci.nih.gov/iam/>
- CTEP Associate Registration and IAM Account Help: [[contact]](mailto:[contact])
- IB Coordinator: [[contact]](mailto:[contact])
- PMB email: [[contact]](mailto:[contact])
- PMB phone and hours of service: [contact] Monday through Friday between 8:30 am and 4:30 pm (ET)

**11.0 MEASUREMENT OF RECURRENCE**

Relapse of disease will be evaluated in this study using CEA testing and radiographic imaging. **An elevated CEA level alone (without radiographic or pathologic evidence of disease) does not qualify as relapsed disease.** For patients who have signs or symptoms for which imaging is clinically indicated, the decision of timing of radiographic studies remains at the discretion of the treating clinician. However, for asymptomatic surveillance after the completion of FOLFOX, the timing of CEA testing and radiographic imaging has been standardized (see [Section 5.0](#)).

**11.1 Schedule of Evaluations**

For the purposes of this study, patients should be reevaluated for recurrence at the following intervals:

- Radiographic Imaging: every 6 months (+/- 1 month) for the first 2 years after registration, then yearly for an additional 3 years (i.e. years 3-5 after registration). Patients should follow the schedule outlined in the Study Calendar ([Section 5.0](#)).
- CEA Testing: 6 weeks after completion of FOLFOX, then every 6 months (+/- 1 month) for 3 years, then yearly (+/- 1 month) for an additional 2 years. Patients should follow the schedule outlined in the Study Calendar ([Section 5.0](#)). After the end of FOLFOX treatment, the timing of CEA should correspond with the timing of radiographic imaging, where possible, but more frequent testing is at provider discretion.

Supporting documentation of relapse should be submitted per [Section 6.1.1](#).

## 11.2 Guidelines for Evaluation of Recurrence

### 11.2.1 Measurement Methods

All measurements should be recorded in metric notation (i.e. decimal fractions of centimeters) using a ruler or calipers.

The same method of assessment and the same technique should be used throughout the treatment and follow-up phases.

Imaging-based evaluation is preferred to evaluation by clinical examination when both methods have been used at the same evaluation.

### 11.2.2 Acceptable Modalities for Measurable Disease

- **Conventional CT and MRI:** This guideline has defined measurability of lesions on CT scan based on the assumption that CT slice thickness is 5 mm or less. If CT scans have slice thickness greater than 5 mm, the minimum size for a measurable lesion should be twice the slice thickness.

As with CT, if an MRI is performed, the technical specifications of the scanning sequences used should be optimized for the evaluation of the type and site of disease. The lesions should be measured on the same pulse sequence. Ideally, the same type of scanner should be used, and the image acquisition protocol should be followed as closely as possible to that used with prior scans. Body scans should be performed with breath-hold scanning techniques, if possible.

- **Chest X-ray:** Lesions on chest x-ray are acceptable as measurable lesions when they are clearly defined and surrounded by aerated lung. However, CT scans are preferable.

## 11.3 Definition of Relapsed Disease

### 11.3.1 Radiographic Recurrence

On radiologic assessment the following must be present: at least one new malignant lesion, which also includes any lymph node that was normal at baseline.

Whenever possible, radiographic relapsed disease should be confirmed by biopsy.

The use of cytology to confirm the neoplastic origin of any effusion that appears is mandatory to determine progressive disease.

Follow-up colonoscopies should be performed to monitor for relapse, with frequency at the discretion of the treating investigator. However, per current guidelines, follow-up colonoscopies should be performed either annually or every other year in patients with known or suspected Lynch Syndrome, as patients with Lynch Syndrome have increased rates of synchronous primary colon cancers. See [Section 5.0](#) and [Section 6.1](#) for additional details.

Elevated CEA level alone (without radiographic or pathologic evidence of disease) does not qualify as relapsed disease. An elevated CEA should trigger a diagnostic workup.

The primary endpoint of this study is disease-free survival (DFS), defined as the time from randomization to first documentation of disease recurrence (primary tumor relapse) or death. Patients who do not have a DFS event will be censored for DFS at

their last disease assessment date. **Confirmed second primary colon cancer and second primaries of other types do not qualify as relapsed disease and will not be included as an event for the DFS endpoint**, which is consistent with the conduct of recent adjuvant phase III trials.

Recurrence can be defined as presence of primary tumor relapse.

Second primary can be defined as presence of a new secondary type of unrelated cancer.

A second primary colon cancer does not represent disease recurrence/relapse from the initially resected primary colon cancer. Recurrences typically occur in close proximity to the surgical anastomosis or at distant sites in the body. Second colon primaries do not involve the surgical anastomosis and can be diagnosed at colonoscopy and confirmed with biopsy. An extracolonic second primary cancer is a tumor that will typically present at a single site that is not believed to represent a recurrence or metastasis from the primary tumor. Both second primaries and extracolonic tumors are increased in patients with Lynch Syndrome, where the most common extracolonic cancer is endometrial cancer, although other potential sites include, but are not limited to, the small intestine and renal collecting system. **If an extracolonic cancer is suspected, biopsy is recommended whenever possible.** Based upon the medical literature, the risk of second primaries during the limited period of follow-up during this adjuvant trial is relatively low in the Lynch Syndrome population.

In the event that the local treating investigator determines that a disease recurrence is suspected, or a second primary or extracolonic malignancy is suspected, the protocol requires the following documentation to be submitted to Alliance for review by the Study Chair:

- Primary Tumor Relapse (DFS event): imaging report, pathology report (if applicable), colonoscopy report\* (if applicable), operative report (if applicable)
- Suspected Second Primary or Extracolonic Malignancy (not DFS event): pathology report, colonoscopy report\* (if applicable), imaging report (if applicable), and surgical report (if applicable)

**\*If recurrence is observed or suspected on imaging and it has colonic or rectal involvement that is not in close proximity to the surgical anastomosis, then a colonoscopy with biopsy is required to exclude a new primary malignancy in the colorectum.** Female patients with isolated recurrence that involves the uterus should undergo biopsy to exclude a primary endometrial carcinoma which is the most common extracolonic malignancy in patients with Lynch Syndrome.

Determination of a DFS event will be done by the local treating investigator. There will be no independent central review. Documentation of patient relapse/new primary will be reviewed by the Alliance Study Chair. Both the assessments of the local investigator and of the Alliance Study Chair will be recorded in the CRF. The primary analysis will be based on the assessment from the local treating investigator.

## 12.0 END OF TREATMENT

### 12.1 Duration of Treatment

Patients who continue to be in remission will continue on therapy for a total of 12 cycles mFOLFOX6 + atezolizumab followed by 6 months of atezolizumab alone if assigned to Arm 1 or 12 cycles mFOLFOX6 in total if assigned to Arm 2. After treatment is completed, patients will be followed per the Study Calendar in [Section 5.0](#).

Disease Recurrence: Remove from protocol therapy any patient with disease recurrence. Document details, including tumor measurements, on data forms. (Patients will be followed for recurrence and survival every 6 months (+/- 1 month) for the first two years after registration, then survival every 6 months and recurrence once annually for years 3-5 after registration, and then survival every 6 months for years 5-8 after registration. Recurrence follow-up will continue per the schedule above for 5 years after registration or until evidence of relapse, whichever comes first. Survival follow-up will continue per the schedule above for 8 years after registration or until death, whichever comes first.)

Discontinuation of Study Agent: If the patient discontinues protocol therapy due to reasons other than recurrence, prior to the completion of planned therapy as per [Section 7.0](#), patients should be followed for disease status and survival per the study calendar ([Section 5.0](#)).

Discontinuation of Specimen Submission: If the patient discontinues protocol therapy for any reason, specimens should continue to be collected and submitted after discontinuation of adjuvant therapy per [Section 6.2](#).

### 12.2 Managing Ineligible Patients and Registered Patients Who Never Receive Protocol Intervention

#### Definition of ineligible patient:

A study participant who is registered to the trial but does not meet all of the eligibility criteria is deemed to be ineligible.

#### Follow-up for ineligible patients who continue with protocol treatment:

Patients who are deemed ineligible after registering may continue protocol treatment, provided the treating physician, study chair, and executive officer agree there are no safety concerns if the patient continues protocol treatment. All scans, tests, and data submission are to continue as if the patient were eligible. Notification of the local IRB may be necessary per local IRB policies.

#### Follow-up for ineligible patients who discontinue protocol treatment:

For patients who are deemed ineligible after registering to the trial, who start treatment, but then discontinue study treatment, the same data submission requirements are to be followed as for those patients who are eligible and who discontinue study treatment.

#### Follow-up for patients who are registered, but who never start study treatment:

For all study participants who are registered to the trial but who never receive study intervention (regardless of eligibility), the follow-up requirements are specified below.

Baseline, off-treatment, and post-treatment follow up (i.e. relapse, recurrence, and survival) data submission required. See the Data Submission Schedule accompanying the All Forms Packet.

### 12.3 Extraordinary Medical Circumstances

If at any time the constraints of this protocol are detrimental to the patient's health and/or the patient no longer wishes to continue protocol therapy, protocol therapy shall be discontinued. In this event:

- Document the reason(s) for discontinuation of therapy on data forms.
- Follow the patient for protocol endpoints as required by the Study Calendar.

### 12.4 Survival Follow-up

Patients will be followed for survival every 6 months (+/- 1 month) for 8 years after registration or until death, whichever comes first.

### 12.5 Lost to Follow-Up

A patient can be deemed lost to follow-up after two years and at least 3 unsuccessful documented attempts to contact the patient. The two-year period starts on the last successful contact of the patient. All attempted patient contacts must be documented in the patient's research record. The attempted contacts must be recorded in Rave as "no contact" and complete the Lost to Follow-up form after two years of no contact.

## 13.0 STATISTICAL CONSIDERATIONS

This study is a two-arm randomized phase III trial comparing the outcomes of patients with stage III colon cancer whose tumors have dMMR status treated with 1) mFOLFOX6 alone and 2) mFOLFOX6 with atezolizumab and its continuation as monotherapy. Patients will be randomized in 1:1 fashion to either mFOLFOX6 alone or mFOLFOX6 with atezolizumab. Efficacy analyses will be based on the intention to treat principle and all randomized patients (including adult and patients aged <18 years) will be included for the analysis i.e. patients will be assigned to the treatment group they were randomized to regardless of the actual treatment received. Analysis related to adverse events will be based on the safety population. All patients who were randomized and received any amount of protocol therapy will be considered evaluable for safety and patients will be assigned to the treatment group they actually received.

### 13.1 Study Endpoint

#### 13.1.1 Primary Endpoint

The primary endpoint of this study is the disease-free survival (DFS), defined as the time from randomization to first documentation of disease recurrent or death. Patients who do not have a DFS event will be censored for DFS at their last disease assessment date. Confirmed second primary colon cancer and second primaries of other types will not be included as an event for the DFS endpoint.

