A Drug dosages need not be changed unless the calculated dose changes by  $\geq 10\%$ , however, if the site recalculates the dose for a lower percentage dose changes (i.e. dose changes that are  $< 10\%$ ) to adhere to institutional policy, then this will not be considered a protocol deviation.

B Patients who did not receive a colonoscopy to the cecum prior to surgery are required to have a full colonoscopy no later than 6 weeks after the completion of chemotherapy, but exact timing within the specified window is per treating physician discretion. If recurrence is observed or suspected on imaging and it has colonic or rectal involvement that is not in close proximity to the surgical anastomosis, then a colonoscopy with biopsy is required to exclude a new primary malignancy in the colorectum. Colonoscopy and pathology reports from all additional colonoscopies performed during the treatment and follow-up periods should be submitted if possible. See [Section 11.3.1](#) for details on follow-up and Lynch Syndrome.

C Perform only on Day 1 of Cycle 1 and Day 1 of Cycle 7.

D Baseline abdominal/pelvic scans can include either: 1) a CT ABD/PELV, or 2) a MRI ABD/PELV. Chest imaging can be either chest CT or chest MRI. CT scans should be of diagnostic quality and performed with oral and IV contrast unless there is a medical contraindication. MRIs should be performed with IV contrast unless there is a medical contraindication. Supporting documentation is to be submitted, per [Section 6.1.1](#).

- E The same imaging modality used at baseline must be used for all subsequent scans. Every 6 months (+/- 1 month) for the first 2 years after registration, and then annually (+/- 3 months) for years 3-5 after registration or until evidence of relapse, whichever comes first. Imaging and reports are to be submitted per Section 6.3. Upon relapse documented by imaging, reports should be submitted for retrospective review by Study Chair per [Section 6.1.1](#).

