### 5.1 Vital Status (Survival)

To ensure current and complete survival data are available, updated vital status (survival) may be requested by the Alliance. The primary focus of a vital status (survival) determination is to identify if a trial participant is deceased.

In support of regulatory requests to minimize missingness for safety and overall survival analysis, public record searches to obtain vital status (survival) for participants who withdrew consent from study or who were lost to follow-up may be requested by the Alliance.

Per FDA Guidance: Data Retention When Subjects Withdraw from FDA-Regulated Clinical Trials (October 2008): If a subject withdraws from the interventional portion of a study and does not consent to continued follow-up of associated clinical outcome information, the investigator must not access for purposes related to the study the subject's medical record or other confidential records requiring the subject's consent. However, an investigator may review study data related to the subject collected prior to the subject's withdrawal from the study, and may consult public records, such as those establishing survival status.

A public record search would utilize information about the participant, from the time the participant consented to the study, to obtain an updated vital status (survival). No participants should be contacted during a public record search by the site research team.

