**Analysis Plan:** DFS will be compared between treatment arms using the stratified log rank test at one-sided level 0.025. The stratification factors listed in [Section 4.6](#), as collected at the time of randomization in OPEN, will be used for the analysis. If there are zero DFS events observed in any of the strata, unstratified log-rank test will be used. If zero DFS events are observed in a certain stratum at an interim analysis and unstratified log-rank is used, all subsequent analyses for DFS will use unstratified log-rank test. The HR for DFS will be estimated using a Cox proportional hazards model and the 95% CI for the HR will be provided. If a stratified log-rank test is used, stratified HR will be considered, and if an unstratified log-rank test is used, unstratified HR will be considered. Kaplan-Meier methodology will be used to estimate the median DFS for each treatment arm, and Kaplan-Meier curves will be produced. Brookmeyer-Crowley methodology will be used to construct the 95% CI for the median DFS for each treatment arm (Brookmeyer and Crowley 1982).

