#### **Sensitivity Analysis Plan:**

- 1) One additional censoring rule will be added for missed disease assessments. For patients with a DFS event who missed one or more scheduled assessments immediately prior to the DFS event, the DFS event will be censored at the last tumor assessment prior to the missed disease assessment.
- 2) For patients with a DFS event who missed one or more scheduled disease assessments immediately prior to the DFS event, the DFS event will be dated on the earliest missed assessment (after the last known tumor assessment). This sensitivity analysis is aimed to assess the impact of missing disease assessment.

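### Once recurrence surveillance ends, only patients who later die stay at risk for DFS, so the Kaplan-Meier tail and median can be false, although the hazard ratio at 165 events barely moves

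*Combined protocol and SAP*

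**What the plan says.** Section 13.1.1 gives DFS as "defined as the time from randomization to first documentation of disease recurrent or death". It sets no limit on when a death counts, and adds: "Patients who do not have a DFS event will be censored for DFS at their last disease assessment date". Section 11.3.1 repeats both rules.

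The two components are followed for different lengths of time:

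- **Recurrence**, section 12.1: "Recurrence follow-up will continue per the schedule above for 5 years after registration or until evidence of relapse, whichever comes first". Study Calendar footnote E schedules the later imaging "then annually (+/- 3 months) for years 3-5 after registration or until evidence of relapse", so the last scheduled scan can fall up to about 5.25 years.
- **Death**, section 12.4: "Patients will be followed for survival every 6 months (+/- 1 month) for 8 years after registration or until death, whichever comes first". Section 5.1 also allows "public record searches to obtain vital status (survival) for participants who withdrew consent from study or who were lost to follow-up".

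Section 13.4.1 plans the summary: "Kaplan-Meier methodology will be used to estimate the median DFS for each treatment arm, and Kaplan-Meier curves will be produced", with Brookmeyer-Crowley limits for the median. Both sensitivity analyses there apply only "For patients with a DFS event who missed one or more scheduled assessments immediately prior to the DFS event".

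No section says how a death after the end of recurrence follow-up enters DFS. Disease assessment is not defined either. Section 11.0 names CEA testing as well as imaging as ways in which relapse is evaluated.

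**The concern.** Take two patients who are clear at the year-5 scan. One is alive at year 7 and is censored at about 60 months. The other dies at 66 months, stays in the risk set until then and is an event. Membership of the late risk set therefore depends on a future outcome, which Kaplan-Meier and Cox methods assume does not happen. OS avoids the problem because section 13.1.2 censors survivors when last known alive.

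The sensitivity analyses do not help here. After surveillance ends no assessment is scheduled, so none can be missed. What is at stake is the published DFS curve and median and, if many such deaths accumulate, the hazard ratio.

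**Working it through.** **1. The plan's own figure.** For HR 0.6, one-sided 0.025 and 90% power, Schoenfeld gives 4(1.960 + 1.282)² / (ln 0.6)² = 161.1, so 162 events. Freedman gives (1.6/0.4)²(1.960 + 1.282)² = 168.1, so 169. The stated 165 lies between them. Expected events with 700 patients, 3.24 years' accrual, 2.05 years' minimum follow-up and 1.25% yearly dropout are 165.2. The figure reproduces.

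**2. Where the true curves stand.** The control hazard is −ln(0.75)/3 = 0.0959 per year. The experimental hazard is 0.6 × 0.0959 = 0.0575.

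- Year-5 DFS: exp(−0.0959 × 5) = 0.619 and exp(−0.0575 × 5) = 0.750.
- Medians: ln 2/0.0959 = 7.2 years and ln 2/0.0575 = 12.0 years.

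On the plan's assumptions neither true median falls within surveillance, so a median reached shortly after year 5 is an artefact.

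**3. Why the curve can hit zero.** If k patients remain in an arm after its last censoring time and all k later die, the remaining factors are (1 − 1/k)(1 − 1/(k−1)) … (1 − 1/1) = 0. One late death after the last censoring is enough.

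**4. When surveillance ends.** Imaging: 5 years plus 3 months = 5.25 years. CEA: 12 cycles × 2 weeks + 6 weeks = 30 weeks, about 0.6 years, plus 3 + 2 years = about 5.6 years. The end point depends on what counts as a disease assessment.

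**5. Planned calendar.** Maximum follow-up is 3.24 + 2.05 = 5.29 years. Patients past year 5: 700 × 0.29/3.24 = 63, by 0.145 years on average. Event-free time past year 5, ignoring dropout: 63 × 0.145 × (0.619 + 0.750)/2 = about 6.2 person-years. At an assumed 0.5-3% yearly death rate this gives 0.03-0.19 deaths. Simulated HR and power were unchanged, and the curve reached zero in 1-8% of runs per arm. Both interim analyses come earlier.

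**6. At 165 events.** The rule was simulated as written: 350 per arm, the hazards above, 1.25% yearly dropout, scans at 6, 12, 18, 24, 36, 48 and 60 months, deaths seen to year 8. Assumed, not in the documents: non-recurrence death 0.5-2% per year, death after recurrence 25% per year, accrual 3.24-4.5 years. Recurrence is documented only at a scan, so the 165th event comes later than 5.29 years. With 1% non-recurrence death:

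| Accrual (years) | Late deaths | HR as written | HR, late deaths excluded |
|---|---|---|---|
| 3.24 | 0.4 | 0.607 | 0.607 |
| 4 | 1.0 | 0.597 | 0.596 |
| 4.5 | 1.4 | 0.616 | 0.614 |

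Across all the assumed rates there were 0.3-2 late deaths, the HR shifted by at most about 0.002, and the curve reached zero in 19-64% of arms. With late deaths excluded it did so in 5-10%.

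**7. Slower events or longer follow-up (hypothetical).**

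- Control 3-year DFS 80%, 4.5 years' accrual, cut-off at 8 years (162-169 events; deaths without documented recurrence 0.5-2% per year): 2-8 late deaths, HR 0.607-0.612 v 0.604-0.607, power at most 1.2 points lower, curve at zero in 56-98% of runs.
- Control 3-year DFS 85%, 4.5 years' accrual, cut-off at 9.5 years (deaths 1-2% per year): 8-16 late deaths, HR 0.607-0.627 v 0.596-0.599, power 2-6 points lower.
- Everyone followed to year 8, under the step 6 model: HR 0.652 v 0.602 if recurrence continues at a constant hazard after year 5, and 0.618 v 0.602 if it stops.

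**The case against.** The strongest reply is that the trial's decision is safe. Section 13.4.1 fixes the DFS analyses at 83, 124 and 165 events, and no DFS re-analysis is planned with the final OS analysis. Under the plan's hazards the log-rank decision does not change, and what remains concerns the end of the curve. That stands for the test. It does not dispose of the curve and the median, which are themselves planned outputs.

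A reader might infer four stronger points that the documents do not support.

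- **That the hazard ratio is diluted in general.** This needs slow events or extended DFS follow-up, and its size depends heavily on assumed recurrence after year 5.
- **That censoring falls at year 5 at the latest.** The scan window and the CEA schedule run later. Section 11.0 also allows symptom-driven imaging, and section 11.3.1 leaves colonoscopy frequency to the investigator.
- **That patients lost before year 5 and later found dead escape every safeguard.** They have missed scheduled assessments, so the first sensitivity analysis censors them before the gap and the second re-dates the event. The primary analysis still carries them, but they are partly addressed.
- **That the DFS analysis certainly includes patients past year 5.** The April 2018 grading date, German last patient in (March 2022) and an August 2024 reporting table suggest a longer calendar. No section gives a first-patient date or a DFS data cut-off.

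It is also fair that changing a primary endpoint in an ongoing trial is more than a wording edit. The second option under the fix answers this.

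**Conclusion.** The asymmetry is in the text, and following the rule as written leaves a late risk set made up only of future decedents. The consequence is a Kaplan-Meier curve that can fall to zero and a median that can be falsely reached: roughly 20-60% of arms reach zero at 165 events, depending on accrual and the assumed death rates. The primary hazard ratio and log-rank decision are essentially unaffected, both at the planned 5.29 years and at 165 events under the plan's hazards. Dilution of about 0.01-0.05 belongs to slow-event scenarios or hypothetical long-term updates. The non-recurrence death rate, the post-recurrence death rate, accrual beyond 3.24 years and recurrence after year 5 are all assumptions. The point is worth correcting because the remedy is cheap. It gives no reason to doubt the sample size or the event target.

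**What to change.** First, define disease assessment in 13.1.1: say whether CEA alone, colonoscopy or unscheduled imaging counts. Then take one of two routes.

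1. **Amend the definition.** State in 13.1.1 that DFS is evaluated through the end of scheduled recurrence surveillance, meaning the year-5 assessment plus its 3-month window. Event-free patients are censored at their last disease assessment within that period. A later death without documented recurrence counts in OS only and not towards the 83, 124 or 165 DFS events.
2. **Leave the primary definition alone.** Pre-specify the same rule as a third DFS sensitivity analysis in 13.4.1, and truncate the displayed DFS curve and the median estimation at that time.

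Under either route, print numbers at risk. In 5-10% of simulated arms the curve still reached zero with late deaths excluded, so its last part should be read with care.

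The cost is SAP wording and a derivation rule. Under the first route a few late deaths leave the DFS count, so 165 events may come slightly later, and an ongoing trial's primary definition changes. Under the second no events are lost. Sample size and event targets stay as they are.
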